## **12.12. Analyses for the Sparsentan + SGLT2 Inhibitor Sub-study**

Sub-study data analysis will be conducted after approximately 60 patients completed the Sub-study.

Safety and efficacy endpoints for the Sub-study will be summarized using descriptive statistics and will be presented by the Sub-study randomized treatment group and overall based on the Sub-study Analysis Set.

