**Open-label Extension Period Endpoints:**

Endpoints for the open-label extension period include, but are not necessarily limited to the following:

- The absolute and percent change from Week 114 in eGFR at each visit.
- The percent change from Week 114 in UP/C at each visit.
- Changes from Week 114 in QoL at each visit.
- Changes from Week 114 in body weight, vital signs, physical examinations, peripheral edema, and clinical laboratory parameters.
- Changes from Week 114 in lipid profile (total cholesterol and triglycerides, low-density lipoprotein, and high-density lipoprotein).
- The incidence of TEAEs during the open-label extension period.

NAME OF COMPANY: Traverse Therapeutics, Inc.
	
NAME OF FINISHED PRODUCT: sparsentan tablets

Sparsentan + SGLT2 Inhibitor Sub-study:
 
For the Sub-study, the baseline visit (Day 1) is defined as the visit upon which eligibility is assessed.
 
Safety Endpoints:
 
Safety evaluations include the following:
 
 
• Changes from Sub-study baseline in body weight, vital signs, physical examinations, peripheral edema, and clinical laboratory parameters at each visit.
 
• The incidence of TEAEs during the Sub-study period.
 
 
Efficacy Endpoints:
 
Endpoints include, but are not limited to:
 
 
• The mean change from Sub-study baseline in UP/C and UA/C based on a 24-hour urine sample at the next scheduled visit.
 
• Achievement of urinary protein excretion <0.3 g/day at the next scheduled visit.
 
• Change in absolute and percent change from Sub-study baseline in eGFR at the next scheduled visit.
 
	

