### **5.3. Sparsentan + Sodium-glucose cotransporter-2 (SGLT2) Inhibitor Sub-study**

The objectives of the Sparsentan + SGLT2 Inhibitor Sub-study, referred to as the Sub-study, are to investigate the safety and efficacy of an SGLT2 inhibitor in combination with sparsentan on proteinuria in patients with IgAN, as compared to sparsentan alone.

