#### **6.1.5.2. Efficacy Endpoints**

Endpoints include, but are not limited to:

- The mean percent change from Sub-study baseline in UP/C and UA/C based on a 24-hour urine sample at the next scheduled visit.
- Achievement of urinary protein excretion  $<0.3$  g/day at the next scheduled visit.
- Change in absolute and percent change from Sub-study baseline in eGFR at the next scheduled visit.

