#### **8.5. Method of Assigning Patients to Treatment (Randomization)**

This study will be conducted in a double-blind, active-controlled manner. Enrolled patients will be randomly assigned in a 1:1 ratio to sparsentan or the active control (irbesartan) in the double-blind period, based on a predefined randomization code (generated by the Sponsor or designee) via the interactive randomization technology (IRT) at the Day 1/Randomization visit. Randomized patients will be stratified by their screening eGFR value (30 to <60 mL/min/1.73 m^2 and ≥60 mL/min/1.73 m^2) and screening urine protein excretion (≤1.75 g/day and >1.75 g/day).

The Sub-study will be conducted in an open-label, randomized manner. Enrolled patients will be randomly assigned in a 1:1 ratio to receive either SGLT2 inhibitor treatment or no SGLT2 inhibitor treatment, based on a predefined randomization code (generated by the Sponsor or designee) via IRT at the Sub-study Screening/Randomization/Day 1 visit.

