one-sided  $\alpha = 0.02$  and residual error of 5.8 mL/min/1.73 m^2 estimated from a random coefficient analysis of the Leicester University Hospital Registry. The projected treatment effects on the rate of change in eGFR were based on a meta-analysis of clinical studies in IgAN using the methodology presented by Inker ([Inker 2019](#)).

To investigate the safety and efficacy of SGLT2 inhibitors in combination with sparsentan on proteinuria in patients with IgAN, as compared to sparsentan alone, approximately 30 patients in each of the two treatment groups (total 60 patients) will be enrolled in the Sub-study. The sample size of the Sub-study is determined empirically without formal statistical assumptions.

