## **12.7. Efficacy Analyses**

Efficacy analyses during the double-blind period will be based on the FAS. The primary and key secondary endpoint analyses only will be repeated in the PP Analysis Set as supportive analyses.

As UP/C is a highly right-skewed variable, analyses will be performed on log-transformed data.

The eGFR for each time point (visit) will be determined using the CKD-EPI (Levey 2009) formula for adults based on age, sex, race, and serum creatinine values from the visit. The eGFR will be determined at screening and at assessment time points detailed in the Schedules of Study Events (Section 15.1).

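### For the randomized SGLT2 inhibitor Sub-study, the protocol pre-specifies only group-wise descriptive statistics: no between-group UP/C estimate or interval, no baseline-adjusted contrast and no settled scale

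*Protocol*

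**What the plan says.** The Sub-study objective in Protocol Section 5.3 is comparative: safety and efficacy of an SGLT2 inhibitor added to sparsentan "on proteinuria in patients with IgAN, as compared to sparsentan alone". Section 8.5 sets the allocation: "Enrolled patients will be randomly assigned in a 1:1 ratio to receive either SGLT2 inhibitor treatment or no SGLT2 inhibitor treatment". Section 12.2 gives the size, "approximately 30 patients in each of the two treatment groups (total 60 patients) will be enrolled in the Sub-study", and adds: "The sample size of the Sub-study is determined empirically without formal statistical assumptions".

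The analysis is in Section 12.12: "Safety and efficacy endpoints for the Sub-study will be summarized using descriptive statistics", presented by Sub-study group and overall. The statistical part of the synopsis repeats it. Section 12.1 lists what descriptive statistics means for a continuous variable: n, mean, standard deviation, median, minimum and maximum.

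The UP/C endpoint appears in two forms. Section 6.1.5.2 has "The mean percent change from Sub-study baseline in UP/C and UA/C"; the synopsis has "The mean change from Sub-study baseline in UP/C and UA/C". For the double-blind period, Section 12.7 says: "As UP/C is a highly right-skewed variable, analyses will be performed on log-transformed data". Section 12.7.1 then adjusts for log baseline UP/C and reports ratios.

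**The concern.** Randomization makes a between-group estimate available, and the objective asks for one, but the stated analysis ends with separate tables for the two groups. A reader who wants the added effect of the SGLT2 inhibitor must set two summaries side by side and judge the gap without an interval.

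The scale is also unsettled. Mean change in UP/C, mean percent change and a ratio of geometric means are three different quantities. Section 12.11, on the extension as a whole, refers to the methods of Sections 12.7 to 12.9. Section 12.12 has no such reference, so the log-scale, baseline-adjusted approach is not carried into the Sub-study. Because the Sub-study is open-label, the choice of scale and estimator is best fixed before results by group are seen.

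**Working it through.** **Is there a planned figure to reproduce?** Not for the Sub-study: its 60 patients have no alpha, power, effect or SD behind them. As a check on the formula, take the main proteinuria calculation in Protocol Section 12.2, with SD of log change 0.92, a 30% reduction (|ln 0.70| = 0.357), two-sided alpha 0.05 and 140 per arm.

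- SE = 0.92 × √(2/140) = 0.110, and 0.357/0.110 = 3.24.
- Power = Φ(3.24 − 1.96) = 0.900, and the required n is 140 per arm.

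The planned 280 patients and 90% power reproduce.

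**Effect of the scale.** Suppose log change in a group is normal with standard deviation SD and the true geometric mean ratio to baseline is g. The expected arithmetic mean percent change is 100 × (g × exp(SD²/2) − 1).

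| SD of log change (assumed) | exp(SD²/2) | g = 0.70 | g = 1.00 |
|---|---|---|---|
| 0.60 | 1.197 | −16.2% | +19.7% |
| 0.92 | 1.527 | +6.9% | +52.7% |

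A group whose geometric mean falls by 30% can therefore show a mean percent change anywhere from a modest fall to a small rise, depending only on the spread. A comparison group with no true change is inflated too. The difference in mean percent change would be −16.2 − 19.7 = −35.9 points at SD 0.60 and 6.9 − 52.7 = −45.8 points at SD 0.92. The direction is preserved, but the size depends on the SD although the true ratio is 0.70 in both cases.

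**Precision of a ratio with 30 per arm.** The 95% CI is the estimate multiplied and divided by exp(1.96 × SD × √(2/30)), where √(2/30) = 0.2582. With log baseline as covariate and equal variances at the two visits, the variance relative to the change score is (1 + r)/2, where r is the baseline to follow-up correlation on the log scale. This is 0.75 at r = 0.5 and 0.85 at r = 0.7, so the log-scale interval is multiplied by 0.866 or 0.922.

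| SD (assumed) | Unadjusted factor | Adjusted, r = 0.5 | Adjusted, r = 0.7 |
|---|---|---|---|
| 0.5 | 1.29 | 1.24 | 1.26 |
| 0.92 | 1.59 (1.61 with t, 58 df) | 1.50 | 1.54 |

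Adjustment narrows the log-scale interval by about 8% to 13%. For example, an observed ratio of 0.70 at SD 0.92 has an unadjusted t-based interval of 0.44 to 1.13.

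The SD of 0.92 is a planning value for Week 36 of the double-blind period, not for 12 weeks on stable sparsentan. The values 0.5 and 0.60, and both correlations, are not in the documents. The figures show a range and do not correct a stated number.

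**The case against.** The strongest defence is that description is the declared design: 60 open-label patients, a size chosen without formal assumptions, and an objective to investigate. No regulatory claim rests on the result, and randomization permits a modelled contrast without requiring one. This rules out any demand for a hypothesis test. Power for a 30% effect at 30 per arm would run from only 0.32 at SD 0.92 to 0.93 at SD 0.40. It does not count against an estimate with an interval, which is what keeps a small comparison from being over-read.

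Second, the detail may lie elsewhere. Section 12.1 calls the protocol text an outline and promises a fuller SAP. The supplied SAP follows Amendment 5 and does not mention the Sub-study, which came with Amendment 6. Extension results are deferred to a separate SAP that was not available. A reader might infer that the Sub-study will produce no contrast at all; the documents do not show that. They show only that Section 12.12 specifies none and points to no other section or plan.

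Two further readings go too far. One is that baseline UP/C is ignored: a change score uses it, and only covariate adjustment is missing. The other is that readers would see raw means alone: the median is in the standard list, and SAP Section 6.1 adds geometric means for UP/C. That SAP predates the Sub-study, so its convention cannot be assumed to apply.

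**Conclusion.** The point holds as a gap in pre-specification. A randomized comparison with a comparative objective has no stated between-group estimate, interval, log scale or baseline-adjusted contrast for UP/C, and its endpoint is defined in two ways that need to be reconciled whatever is decided about modelling.

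The scale matters more than the covariate. Under a normal log change, a 30% geometric mean reduction corresponds to an expected mean percent change of about −16% (SD 0.60) to +7% (SD 0.92), while adjustment narrows the interval by only about 8% to 13%. These sizes depend on assumed SDs and correlations. A reader might infer that the planned summary could make a benefit look like harm against the comparison group. The calculation does not support that, because with equal spread both groups are inflated and the direction is kept; what is lost is an interpretable size.

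This is a worthwhile, low-cost improvement. It does not affect the main trial's conclusions.

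**What to change.** Define the UP/C endpoint once, as the ratio of the 12-week value to Sub-study baseline, and use that definition in both the synopsis and Section 6.1.5.2.

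In Section 12.12, or in the extension/Sub-study SAP with a reference from 12.12, state that log UP/C at the 12-week Sub-study visit is analysed by ANCOVA with randomized Sub-study group and log Sub-study baseline, on the Sub-study Analysis Set. Report the geometric mean ratio with its 95% CI as estimation only, with no test, and keep the descriptive tables.

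Do not extend this to UA/C yet. Both versions of the endpoint include UA/C, but the extension 24-hour urine is assayed only for protein excretion and creatinine (Table 15.1-3 footnote g, Table 15.1-4 footnote e, Table 15.2-2), and Table 15.1-5 sends the Sub-study to the extension schedule. Without urine albumin the ratio cannot be formed, so the UA/C endpoint and the assay list must be reconciled first.

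The UP/C change costs a few lines of text and minor programming. It needs no additional patients or visits and uses no alpha.

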### **13. SPECIAL REQUIREMENTS AND PROCEDURES**

This protocol was designed and will be conducted, recorded, and reported in compliance with the ICH Harmonised Tripartite Guidelines for GCP, 1996; ICH Guidelines for Safety Data Management, 1994; the US Code of Federal Regulations (CFR 21 Parts 50, 56, and 312); and the European Union Clinical Trials Directive, 2001/20/EC. The protocol meets legal and regulatory requirements according to the country of conduct.

#### **13.1. Institutional and Ethics Review**

This protocol and associated ICF, patient information sheet, any information provided to the patient, the Investigator's Brochure, and any proposed advertising material will be submitted to an appropriate IRB/IEC, applicable regulatory authorities, and host Institution(s) for written approval (where applicable). These documents will also be submitted to, and approved by, the above parties for all amendments to the original approved documents (where applicable). Documentation of any applicable approval(s) and the approved ICF will be received by the Sponsor or its designee prior to enrollment of patients and release of study medication.

#### **13.2. Data Monitoring Committee**

This study will employ an independent DMC that may include nephrology, internal medicine, statistician(s), and/or pharmacovigilance physicians. The DMC members will not be involved in the study as Investigators or consultants. The DMC will have study conduct oversight as defined by the DMC charter. All members will have considerable experience with clinical study conduct and DMCs. Any candidate found to have a financial, intellectual, or personal conflict of interest, or whose name is listed on the FDA debarment list, will not be offered membership. Conflicts of interest will be assessed regularly, and if members are found to have a new conflict of interest, they will be replaced.

The DMC will meet approximately bi-annually at scheduled meetings but may agree to adjust meeting frequency based upon actual and projected data availability. In addition, ad hoc meetings may be convened, as appropriate, to review safety data. Based on review of available data, the DMC will advise the Sponsor on the validity and scientific merit of continuing the study. Adjustments to or stopping of the protocol-defined doses may be considered based on DMC evaluation of safety and tolerability data.

Written minutes of both open and closed DMC sessions will be prepared. The minutes of closed sessions will be made available to the appointed Sponsor designees only after the database is locked and all data are unblinded.

The DMC may request unblinded individual patient data as appropriate. Data reviewed during the meetings will include, at a minimum, disposition, demographics, exposure, clinical laboratory results, MedDRA-coded AEs, and AEs leading to early treatment discontinuation. At each meeting, detailed narratives of interval SAEs (including events resulting in death) are reviewed by the DMC in addition to a cumulative list of all SAEs.

All Investigators and responsible IRBs/IECs will be informed of any decisions made by the Sponsor based on recommendations from the DMC relating to patient safety that alter the conduct of this study. The Investigators will inform patients of such actions, and the protocol and ICF will be revised, as appropriate.

### **13.3. Changes to the Conduct of the Study or Protocol**

Any changes to the study protocol, such as changes in the study design, objectives or endpoints, inclusion and exclusion criteria, and/or procedures (except to eliminate an immediate hazard) will be implemented only after approval by the Sponsor or its designee. All protocol changes will be documented in protocol amendment(s). Protocol amendment(s) (excluding urgent safety amendments) will be signed by the Investigator and approved by the IRB/IEC and regulatory agencies (where required) prior to implementation. Any changes in study conduct that result from a pending amendment will be considered protocol deviations and should be reported to the IRB/IEC. Documentation of IRB/IEC approval will be returned to the Sponsor or its designee.

### **13.4. Investigator's Responsibilities**

The Investigator agrees to:

- Conduct the study in accordance with the protocol and make changes only after receiving written approval from the Sponsor or its designee, except to protect the safety, rights, or welfare of patients.
- Personally conduct or supervise the study.
- Ensure that requirements related to obtaining informed consent and IRB/IEC review and approval comply with ICH E6, CFR 21 Parts 50 and 56, and local laws.
- Report to the Sponsor or its designee any AEs that occur during the study in accordance with ICH E6, CFR 21 Part 312.64, and local laws.
- Read and understand the Investigator's Brochure, including potential risks and side effects of the investigational product (study medication).
- Ensure that all associates, colleagues, and employees assisting in the conduct of the study are informed of their obligations in meeting the above commitments.
- Maintain adequate records in accordance with ICH E6, CFR 21 Part 312.62, and local laws and have records available for inspection by the Sponsor, FDA, or other authorized agency.
- Ensure that the IRB/IEC complies with requirements of ICH E6, CFR 21 Part 56, and local laws and will be responsible for initial and continuing review and approval of the clinical study.
- Promptly report to the IRB/IEC and the Sponsor or its designee all changes in research activity and unanticipated problems involving risks to patients or others (including amendments and expedited safety reports).
- Comply with all other requirements regarding obligations of Investigators and all other pertinent requirements listed in ICH E6, CFR 21 Part 312, and local laws.
- Provide progress reports and notifications of SAEs to the IRB/IEC according to local regulations and guidelines.

#### **13.4.1. Patient Informed Consent**

Investigators agree to adhere to GCP, which includes ethical principles that have their origin in the Declaration of Helsinki, when developing the ICF and when obtaining consent from the patient. Written informed consent is required prior to enrollment in the study. It is the responsibility of the Investigator to document the consent process within the source documents and obtain consent using an IRB/IEC-approved consent form.

The Investigator will ensure that each patient is given full and adequate oral and written information about the nature, purpose, possible risks, and benefits of the study as well as potential treatment alternatives. Patients will be notified that they are free to discontinue participation in the study at any time and will be given the opportunity to ask questions and allowed time to consider the information provided. A copy of the signed ICF will be provided to the patient.

A separate signed ICF will be obtained from patients who participate in the open-label extension period. A separate signed ICF will be obtained from patients who participate in the Sub-study.

If necessary, due to the challenges related to the COVID-19 pandemic, a patient may provide informed consent remotely (ie, via telephone, email, etc.), as dictated by local public health authority requirements. It is the responsibility of the Investigator to document this consent process within the source documents. The patient must also provide a manually signed copy of the ICF as soon as reasonably possible, either by mail or at the next site visit.

#### **13.4.2. Case Report Forms**

Copies of pertinent records in connection with the study, including all source documents, will be made available to the Sponsor or its designee upon request with due precaution toward protecting the privacy of the patient.

Data will be entered by the site onto the eCRFs in the Electronic Data Capture system or downloaded from a device, in the case of patient outcomes. Unless explicitly directed, blank data fields are not acceptable. Any erroneous entries made on the eCRFs will be corrected by the site. Changes made to the data after initial entry into the eCRF will be captured via an electronic audit trail and include the reason for change. Incomplete entries or entries needing additional explanation will be queried to the site for clarification.

#### **13.4.3. Record Retention**

The Investigator is responsible for oversight and maintenance of the study records and patient source documents. These records will be readily available for audit or inspection.

The Investigator will retain study records for at least 2 years after the last marketing approval has been granted and there are no pending marketing applications in an ICH region, or until at least 2 years have elapsed since the formal discontinuation of the clinical program. However, these documents should be retained for a longer period, if required by other applicable requirements (eg, applicable local regulatory requirement) or by an agreement with the Sponsor or its designee. The Investigator will contact the Sponsor or its designee prior to any record destruction.

Patient records or other source data will be kept for the maximum period of time mandated by the hospital, Institution, or private practice, but not less than 15 years.

If off-site archiving is used, all records will be retrieved and made available for review at the time of an audit or regulatory authority inspection.

#### **13.4.4. Monitoring**

A representative of the Sponsor or its designee will visit the Investigator periodically for the purpose of monitoring the progress of this study in accordance with the protocol, GCP, and local regulations. Non-compliance with the protocol, GCP, and local regulations will be documented, and corrective actions implemented, if necessary. It is the responsibility of the Investigator to be present or available for consultation during monitoring visits. During these routine visits, all data pertaining to a patient's participation in this clinical investigation will be made available to the Study Monitor. The Investigator will comply with applicable privacy and security laws for use and disclosure of information. Study Monitors will perform source document verification according to the clinical monitoring plan to ensure consistency between the eCRFs and source documents. Discrepancies will be resolved in accordance with the principles of GCP.

If necessary, due to the challenges related to the COVID-19 pandemic, monitoring activities may be performed remotely as dictated by local public health authority requirements.

At any time prior to, during, or after completion of the clinical study, an audit may be performed on a study site by the Sponsor or its designee, an IRB/IEC, or a representative of a national regulatory agency. Investigators will notify the Sponsor or its designee upon notification of inspection by a representative of a national regulatory agency. A Sponsor or designee representative will be available to assist in the preparation for study site inspections. All pertinent study data will be made available for verification, audit, or inspection purposes.

